5.1.1.2.3 Significant Protocol Deviations

Protocol deviations and significance classification will be defined in the protocol deviation requirements specification document. Unique participants reporting significant protocol deviations will be summarized in total and by indication as follows:

Table 5–8 Protocol Deviation Summary

Parameter	Description	Timing	Methodology
Significant protocol	Overall summary and by protocol	_	Categorical
deviations	deviation term		descriptives

5.1.1.2.4 Demographics

Demographics will be summarized in treated and non-treated groups for the Screened Population, in total and by indication for the Safety and ITT populations, and in total and by treatment group within each indication for the Double-blind ITT Population as follows:

Table 5-9 Demographic Summaries

Parameter	Description	Timing	Methodology
Age	Age (years) relative to informed consent date	Informed consent	Continuous descriptives
Age group	 < 40 years ≥ 40 - < 65 years ≥ 65 years 	Informed consent	Categorical descriptives
Sex, race, race group, and ethnicity	 eCRF categories Race group White Non-white 	Screening Period	Categorical descriptives

5.1.1.2.5 Baseline Characteristics

Baseline characteristics will be summarized in total and by indication for the Safety and ITT populations, and in total and by treatment group within each indication for the Double-blind ITT Population as follows:

Table 5–10 Baseline Characteristics Summaries

Baseline characteristics • Height (cm) • Weight (kg) • Body mass index (BMI) • Weight (kg) / height (m)² Baseline efficacy Endpoints fully described in Section 5.1.1.3 • Patient assessment of constipation severity • Patient assessment of IBS symptom severity (IBS-C only) • Degree of relief of IBS symptoms (IBS-C only)	Parameter	Description	Timing	Methodology
 5.1.1.3	Baseline characteristics	Weight (kg)Body mass index (BMI)	on or before	
Summarize only for the ITT population	Baseline efficacy	 Patient assessment of constipation severity Patient assessment of IBS symptom severity (IBS-C only) Degree of relief of IBS symptoms (IBS-C only) 	on or before	

5.1.1.2.6 Medical History

Medical history, encompassing abnormalities and surgeries reported as occurring before the Screening Visit, will be coded using the Medical Dictionary for Regulatory Activities (MedDRA), version 19.0 or newer. Unique participants who report medical history events will be summarized by MedDRA system organ class and preferred term in total and by indication for the Safety Population as follows:

Table 5–11 Medical History Summary

Parameter	Description	Timing	Methodology
Medical history	Abnormalities and surgeries occurring	Screening Period	Categorical
	before the Screening Visit		descriptives

5.1.1.2.7 Prior and Concomitant Medications

Medications will be coded using the World Health Organization (WHO) Drug Dictionary, version March 2016 or newer. Unique participants who reported medications will be summarized by Anatomical Therapeutic Chemical (ATC) 4 class and preferred term in total and by indication for the Safety Population as follows:

Table 5–12 Medication Summaries

Parameter	Description	Timing	Methodology
Prior medications	Medications taken ≥ 1 time before the	Screening Period	Categorical
	treatment start date, regardless of		descriptives

Parameter	Description	Timing	Methodology
	medication end date		
Concomitant medications	Medications taken ≥ 1 time on or after the treatment start date, regardless of medication start date • Medications starting 1 day after treatment end date will be listed but excluded from analysis	Treatment Period	Categorical descriptives

5.1.1.3 Efficacy

Efficacy will be based on the ITT Population unless otherwise specified.

Baseline values for efficacy endpoints are defined as the latest assessment on or before Treatment Day 1. There are no baseline values for treatment satisfaction endpoints.

[figure not shown]
5.1.1.3.1 Efficacy Analyses

[figure not shown]
Efficacy endpoints will be summarized in total and by indication (if applicable) as follows:

Table 5–13 Efficacy Endpoints

Endpoint	Description	Timing	Methodology
Patient assessment of constipation severity	Rating of constipation severity during the previous 7 days on a 5-point ordinal scale • Higher scores indicate greater severity	Weeks 2, 4, 12, 26, 40, 52 ¹	CFB descriptives
Patient assessment of IBS symptom severity (IBS-C only)	Rating of IBS symptoms severity during the previous 7 days on a 5-point ordinal scale • Higher scores indicate greater severity	Weeks 2, 4, 12, 26, 40, 52 ¹	CFB descriptives
Degree of relief of IBS symptoms (IBS-C only)	Rating of degree of relief of IBS symptoms during previous 7 days on a 7-point balanced ordinal scale • Lower scores indicate greater relief	Weeks 2, 4, 12, 26, 40, 52 ¹	CFB descriptives
IBS treatment satisfaction assessment (IBS-C only)	Rating of degree of satisfaction with the study treatment's ability to relieve IBS symptoms on a 5-point ordinal scale • Higher scores indicate greater satisfaction	Weeks 2, 4, 12, 26, 40, 52 ¹	Continuous descriptives
Constipation treatment satisfaction assessment (CIC only)	Rating of degree of satisfaction with the study treatment's ability to relieve constipation symptoms on a 5-point ordinal scale • Higher scores indicate greater satisfaction	Weeks 2, 4, 12, 26, 40, 52 ¹	Continuous descriptives

Analysis visits defined in Section 6.2.

[figure not shown]

[figure not shown]

5.1.1.3.3 Double-blind Treatment Period Analyses

A set of exploratory analyses will be conducted for Double-blind Safety Population participants, unless otherwise specified, for the subset of participants who experience an intolerable AE during the initial Open-label Treatment Period. Data from the Dose-reduced Open-label Treatment Period following discontinuation of double-blind treatment will be excluded from these analyses.

Pre-randomization (Double-blind Treatment Period baseline) values for efficacy endpoints are defined as the latest available assessment during the Treatment Period on or before the Double-blind start date.

[figure not shown]

5.1.1.4 Safety Analyses

Safety analyses will be based on the Safety Population unless otherwise specified.

Baseline values for applicable safety endpoints are defined as the latest non-missing assessment on or before the treatment start date.

[figure not shown]

[figure not shown]
5.1.1.4.2 Adverse Events

[figure not shown]
The following adverse event (AE) terms are defined:

Table 5–20 AE Terms

Term	Description			
Treatment-	An event that meets the following condition:			
emergent	 Treatment start date ≤ event start date ≤ treatment end date + 1 and meets either of the following conditions: 			
	 The same term is never reported before the treatment start date 			
	• The same term is reported before the treatment start date and the term increases in severity on or after the treatment start date			
	 Event severity > maximum severity of same term reported before the treatment start date 			
On-therapy	An event where:			
	• Treatment start date ≤ event start date ≤ treatment end date + 30			

5.1.1.4.6 Immunogenicity

Individual immunogenicity samples will be assayed and categorized as 1 of the following:

- ADA positive
 - Screening result = positive AND confirmatory result for anti-linaclotide antibodies = positive
- ADA negative
 - o Any of the following:
 - Screening result = negative
 - Screening result = positive AND confirmatory result for anti-linaclotide antibodies = negative

- ADA undetermined (sample lost, damaged, out of specifications, insufficient volume)
 - o Any of the following:
 - Screening result = missing
 - Screening result = positive AND confirmatory result for anti-linaclotide antibodies = missing

Baseline ADA status is defined as the assay result of the Treatment Day 1 (Visit 2) pre-treatment sample.

Overall postbaseline ADA status will be derived using all postbaseline samples during the Treatment Period and within 7 days after the treatment end date, and are defined as follows:

Table 5-27 Overall Postbaseline ADA Status Categories

Assessment/Term	Description
Treatment-induced ADA	≥ 1 postbaseline ADA positive sample
positive ¹	
Treatment-boosted ADA	\geq 1 postbaseline ADA positive sample with titer values \geq 4 \times baseline titer value
positive ²	
Non-treatment-boosted ADA	All postbaseline ADA positive samples with titer values $< 4 \times$ baseline titer value
positive ²	and not qualifying as ADA negative
ADA negative	≥ 1 postbaseline ADA negative sample and no postbaseline ADA positive samples
ADA undetermined	Participant with no assessable samples (sample lost, damaged, out of specifications,
	insufficient volume)
	 Missing data considered ADA undetermined

[figure not shown]
¹ Only applicable to baseline ADA negative or ADA undetermined participants

Immunogenicity endpoints will be summarized in total and by indication as follows:

Table 5–28 Immunogenicity Endpoints

Endpoint	Description	Timing	Methodology
Treatment-related ADA positive responder	Meets either of the following criteria: • Treatment-induced ADA positive for baseline ADA negative or ADA undetermined participants • Treatment-boosted ADA positive for baseline ADA positive participants Non-responder otherwise Only includes participants with ≥ 1 assessable postbaseline sample (ADA undetermined excluded)	Treatment Period + 7 days after treatment end date	Immunogenicity responder

² Only applicable to baseline ADA positive participants

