Primary Outcome Measure	ADA determinations from blood samples
Secondary Outcome Measures	AE reporting of recurrence (including date) of intolerable diarrhea after randomization to double-blind treatment following resolution of initial intolerable diarrhea. Assessments of efficacy [REDACTED] during open-label treatment, and during double-blind treatment.
[REDACTED]	[REDACTED]

Statistical Methods
	
Immunogenicity Assessments For each indication separately and combined, the number and percentage of patients meeting treatment-related ADA-positive status will be summarized, along with the 1-sided 95% Clopper-Pearson confidence interval, for Safety Population patients with at least 1 assessable postbaseline sample, ie, patients who are not postbaseline ADA undetermined (sample lost, damaged, or out of specifications). A sensitivity analysis will be performed where baseline ADA undetermined patients are excluded.
 
Efficacy [REDACTED] The efficacy [REDACTED] will be analyzed descriptively based on the Intent-to-Treat Population. As this is an open-label study, no inferential statistics will be performed.
 
[REDACTED]
 
[REDACTED]

-----------------------------------	--

[figure not shown]

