5.1.1.1.3 Statistical Methodology

The methodologies defined below apply as specified to individual endpoints defined in this SAP. When indicated, 95% 2-sided confidence intervals (CIs) and 2-sided p-values will be presented unless otherwise specified.

Table 5–3 Statistical Methodology

Methodology	Description	
Categorical counts	Number of participants in individual categories	
	\circ Participants with ≥ 1 qualifying event counted once per individual category	
Categorical	 Number and percentage of participants in individual categories 	
descriptives	\circ Participants with ≥ 1 qualifying event counted once per individual category	
	• (Optional if specified) N1 if percentage denominator ≠ number of participants in the	
	population (standard percentage denominator)	
	 N1 = participants with non-missing baseline value 	
	_	

Methodology	Description
	 Unevaluable assessments considered missing
	 If specified, participants with baseline PCS values will be excluded
	_
Continuous	• N1, mean, SD, median, minimum, maximum
descriptives	• N1 = participants with non-missing value
CFB descriptives	• Continuous descriptives for baseline, postbaseline, and change from baseline (CFB)
	values
	 N1 = participants with non-missing values at both baseline and the specified
	postbaseline analysis visit
CFB ANCOVA	 Continuous descriptives and SE for baseline, postbaseline, and CFB values
	 Estimates derived from ANCOVA model for CFB value controlling for fixed factors
	(treatment group) and fixed covariates (baseline value)
	Least squares (LS) means and standard errors
	LS mean differences, standard errors, and CIs vs highest LIN dose ¹ Description of the LIN dose of
	 P-values from contrast t-test comparing lower LIN doses² vs highest LIN dose¹
	• N1 = participants with non-missing values at both baseline and the specified
Responder	postbaseline analysis visit
Responder	 Categorical descriptives for responders and nonresponders Nonresponders include:
	Participants who do not meet responder criteria
	 Participants with no postbaseline values
	Risk differences and Wald CIs vs highest LIN dose ¹
	• Unadjusted risk ratios (RRs), odds ratios (ORs), and CIs vs highest LIN dose ¹
	• P-values from Fisher's exact test comparing lower LIN doses ² vs highest LIN dose ¹
Immunogenicity	Categorical descriptives for responders and nonresponders
responder	Nonresponders include:
1	Participants who do not meet responder criteria
	 Participants with no postbaseline values

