	Responder rate 1-sided 95% Clopper-Pearson CIs
	• N1 = all participants unless otherwise specified
Time-to-event	Categorical descriptives for participants with events and censoring
	 Censoring includes:
	 Participants who do not meet event criteria
	 Participants with no postbaseline values
	• Quartiles and CIs derived from Kaplan-Meier (KM) nonparametric model using log-
	log transformation of survivor function
	 Estimates derived from Cox proportional hazards model controlling for factor
	(treatment group)
	o Hazard ratios (HRs) and CIs vs highest LIN dose ¹
	• Estimates derived from log-rank model controlling for factor (treatment group)
	o P-values comparing lower LIN doses ² vs highest LIN dose ¹
173.4.C	N1 = all participants unless otherwise specified
KM figure	• Step-function figure of cumulative distribution function (1 – survivor function)
	estimates with censoring indicators, derived from KM nonparametric model

CFB = change from baseline; ANCOVA = analysis of covariance; TTE = time-to-event.

Methodology Description

Raw and derived data listings will be provided, and will be fully defined in the table, figure, and data listing specification document.

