5.1.1.1.4 Missing Data

General missing data handling conventions are specified for methodologies in Section 5.1.1.1.3 and summarized as follows:

Table 5–4 Missing Data Handling by Endpoint Type

Parameter type	Timing	Missing Data Handling
Responder	Double-blind Treatment Period	 All participants included unless otherwise specified Participants with no postbaseline values = nonresponders
Immunogenicity responder	Treatment Period	Participants with no postbaseline assessable values excluded
Time-to-event	Double-blind Treatment Period	 Participants not reporting specified event (intolerable diarrhea) during the Open-label Treatment Period excluded Participants with no postbaseline values = censored
CFB ANCOVA	Treatment Period	 If missing covariates (including baseline if applicable) Participant excluded If missing derived value at the specified postbaseline analysis visit: Participant excluded

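### Does SAP Table 5-3 put untested patients into the denominator of the primary ADA rate as nonresponders?

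*SAP*

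**What the plan says.** SAP Table 4-1 names treatment-related ADA positive responder as the primary endpoint. Five places bear on who is counted.

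- **SAP 5.1.1.4.6, Table 5-28** defines the endpoint, assigns it the Immunogenicity responder method and restricts it: "Only includes participants with ≥ 1 assessable postbaseline sample (ADA undetermined excluded". Table 5-27 in the same section places missing data in the ADA-undetermined category.
- **SAP 5.1.1.1.3, Table 5-3**, Immunogenicity responder row, lists "Participants with no postbaseline values" under nonresponders and closes with "N1 = all participants unless otherwise specified". The text introducing the table says its methods "apply as specified to individual endpoints defined in this SAP".
- **SAP 5.1.1.1.4, Table 5-4** opens with "General missing data handling conventions are specified for methodologies in Section 5.1.1.1.3 and summarized as follows". Its Immunogenicity responder row reads "Participants with no postbaseline assessable values excluded". Its separate row for the general Responder type, limited to the Double-blind Treatment Period, reads "Participants with no postbaseline values = nonresponders".
- **Protocol synopsis, Statistical Methods**, gives the ADA rate "for Safety Population patients with at least 1 assessable postbaseline sample".
- **SAP 5.1.2 and Protocol 9.7.9** state an upper bound of 0.374% for 0 of 800.

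**The concern.** Read alone, the Table 5-3 row gives the opposite instruction to the endpoint definition that refers to it. A patient with no postbaseline sample cannot be both a nonresponder and outside the analysis. Table 5-4 sharpens the impression: it presents itself as a summary of Section 5.1.1.1.3, yet gives this method a different rule from the one it is meant to summarize.

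The direction matters. For an immunogenicity endpoint, counting an untested patient as a nonresponder means counting that patient as ADA-free. This can only lower the observed rate and its upper bound, which is the reassuring direction, in a study run to meet a post-marketing requirement on ADA development. Had the primary denominator really been left open between the two rules, the plan would need correcting.

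**Working it through.** **Step 1: which rule governs.**

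| Place | Patients with no assessable postbaseline sample | Level |
|---|---|---|
| Table 5-3, nonresponder bullet | nonresponders (those with no values) | generic method |
| Table 5-3, N1 | in the denominator, unless specified otherwise | generic method, yields to the endpoint |
| Table 5-4 | excluded | by endpoint type |
| Table 5-28 | excluded | the primary endpoint itself |
| Protocol synopsis | excluded | protocol |

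Table 5-3 makes its methods subject to what each endpoint specifies, and its N1 line repeats this for the denominator. Table 5-28 does specify otherwise, so the denominator is patients with at least one assessable postbaseline sample.

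**Step 2: whether the difference in wording leaves a gap.** Table 5-3 speaks of no values; the other places speak of no assessable values or samples. Table 5-27 classes missing data as ADA undetermined, and Table 5-28 excludes that category. Patients with no values are therefore a subset of those excluded. Once they are removed, the bullet has nobody to act on. Patients with only undetermined samples cannot return as patients who fail the responder criteria either, because the same exclusion removes them.

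**Step 3: reproduce the plan's figure.** The one-sided 95% Clopper-Pearson upper bound for x positives in n is the 0.95 quantile of Beta(x + 1, n − x). For x = 0 it reduces to 1 − 0.05^(1/n). With n = 800, 1 − 0.05^(1/800) = 0.3738%, which matches the stated 0.374%.

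**Step 4: size if the bullet were misapplied.** The documents give no share of patients without an assessable postbaseline sample, so 1%, 5% and 10% are assumptions, as is the case of 4 positives. The planned total of 800 and the minimum of 300 per indication come from the protocol and SAP.

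| Case | Bullet misapplied | Excluded, 1% missing | Excluded, 5% missing | Excluded, 10% missing |
|---|---|---|---|---|
| Pooled, n | 800 | 792 | 760 | 720 |
| 0 positives: bound | 0.374% | 0.378% | 0.393% | 0.415% |
| 4 positives: rate | 0.500% | 0.505% | 0.526% | 0.556% |
| 4 positives: bound | 1.141% | 1.152% | 1.200% | 1.267% |
| One indication, n | 300 | 297 | 285 | 270 |
| 0 positives: bound | 0.994% | 1.004% | 1.046% | 1.103% |

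With no positives and 10% missing, the gap is 0.415 − 0.374 = 0.041 percentage points pooled, and 1.103 − 0.994 = 0.109 points in one indication at its minimum size.

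**Step 5: how many patients could be affected.** An affected patient must have been dosed and yet have no usable sample from any Treatment Period visit or from early termination. Protocol 9.5.1.1 takes blood at every scheduled Treatment Period visit, asks for a sample within 7 days of the last dose from patients who leave, and allows a repeat draw when the Week 52 or early-termination sample is unusable. These provisions should keep the share low, although the documents do not quantify it.

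**The case for a change.** The strongest case for an edit is that the clause yielding to other specifications is attached to N1, not to the nonresponder bullet. The bullet carries no qualifier, sits in the method assigned to the primary endpoint, and is either inoperative or wrong. A programmer who builds a routine from Table 5-3 alone would score untested patients as ADA-free, and the error would always flatter the product. Removing the line would cost almost nothing.

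Part of this stands. The bullet is a real inconsistency. It matches the bullet in the general Responder row, so it was probably carried over from there, although that is an inference. Deleting it would be reasonable housekeeping whenever the SAP is next opened.

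The rest does not carry. The lead-in to Table 5-3 subordinates the whole method to the endpoint, not only its N1 line. The misreading requires someone to follow a generic row while ignoring the denominator written into the endpoint definition that refers to it, the matching row of Table 5-4 and the protocol. Restating N1 in Table 5-3 adds nothing, because Table 5-28 already sets it.

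**Conclusion.** The concern does not call for a change. A leftover line in a generic methods table conflicts with the endpoint's own definition, and the SAP's rules of precedence settle the matter in favour of exclusion, in agreement with Table 5-4 and the protocol synopsis. The primary denominator is defined and is the appropriate one for a safety rate; deleting the bullet would alter no planned result.

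The bounds for 1%, 5% and 10% missing show only what a misapplication would do: at most 0.041 percentage points pooled with no positives, over an assumed range. The visible text sets no hypothesis test or threshold on the bound, so a shift of that size would not reverse a stated decision rule. The 0.374% for 0 of 800 is correct for 800 assessable patients. The conclusion assumes that the separate table and listing specifications, which are not available here, follow Table 5-28.

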5.1.1.5 Subgroup Analyses

[figure not shown]
Not applicable.

[figure not shown]
5.1.1.6 Interim Analyses

[figure not shown]
Not applicable.

[figure not shown]
5.1.2 Determination of Sample Size

The objective of this study is to assess the long-term safety of linaclotide administered to participants with IBS-C or CIC and to determine the potential of linaclotide to induce ADAs. If 0 of 800 participants develop ADAs, the 1-sided 95% upper CI for this rate (0/800 [0%]) is 0.374%.

[figure not shown]

[figure not shown]

[figure not shown]
Efficacy Endpoint Conventions 6.4

7. References

EuroQol – a new facility for the measurement of health-related quality of life. The EuroQol Group. Health Policy 1990 Dec 16;3:199-208.

Marquis P, De La Loge C, Dubois D, McDermott A, Chassany O. Development and Validation of the Patient Assessment of Constipation Quality of Life Questionnaire. Scandinavian Journal of Gastroenterology 2005;40:540-551.

8. History of Change

Amendment 1: 2018-05-23

Section(s)	Description	Rationale
Global	Corrected case for selected hyphenated words:	Alignment with MW style guidelines
	Dose-reduced	
	Double-blind	
1	Changed sponsor from Forest to Allergan on cover page	Updated NDA holder
	and headers, and changed sponsor address	
3	Removed selected abbreviations and expansion of	Alignment with MW style guidelines;
Global	; Removed instances	abbreviations not required
	of removed abbreviations from SAP body; inclusion of	
	selected references in table footnotes	
5.1.1.1.1	Added All enrolled participants population	Handling of participants who entered
		OL with exposure records not
		indicating treatment was actually taken
5.1.1.2.2	Specified participant disposition based on study design	Clarification
	epochs, not analysis periods	
5.1.1.2.2	For participants who continued to next period, removed	Simplification/elimination of confusion
	"due to AE" clause	
5.1.1.2.3	Specified "significant" protocol deviations	Accuracy
5.1.1.2.5	Changed height unit to cm	Accuracy
5.1.1.3.1	Changed continuous descriptives to CFB descriptives for	Incorrect analysis references
5.1.1.3.2	endpoints with baseline values	
5.1.1.3.3	Changed population to DB Safety for selected analyses	Incorrectly specified in protocol
5.1.1.3.3	Changed assignment of values on same date as DB start	Value from DB start date assumed to
	date from post-rand to pre-rand	be before first DB administration
		Clarification
5.1.1.4.6	Revised details of ADA classification rules; Revised	Clarification
	listing specification	
		Correction
